**Prospective Randomised Clinical Trial Evaluating the Effects
of Two Different Implant Collar Designs on Peri-Implant
Healing and Functional Osseointegration after 25 Years**

ClinicalTrials.gov Identifier: NCT03862482.

University of Montreal Ethics Committee Certificate No.

CERC-19-015-P (Approved May 02, 2019).

Prospective Randomised Clinical Trial Evaluating the Effects of Two Different Implant Collar Designs on Peri-Implant Healing and Functional Osseointegration after 25 Years

ClinicalTrials.gov Identifier: NCT03862482.

University of Montreal Ethics Committee Certificate No. CERC-19-015-P.

Objectives: Evaluate the effects of two different machined-collar lengths and designs on peri-implant healing.

Material and Methods: An implant with a microtextured surface and 3.6mm-long internal-connection machined collar was compared to two implants that had an identical 1.2mm-long external-connection machined collar, but one had the microtextured surface while the other's was machined. Participants received the three implants, with microgap at the crest, alternately at five sites between mental foramen, and a full-arch prosthesis. Peri-implant bone levels were measured after 23 to 26 years of function. Keratinized gingiva height, plaque, probing depth, bleeding, and purulence were also evaluated. Descriptive and mixed models for repeated-measures analyses were used, with Bonferroni correction for pairwise comparisons.

Material and Methods

Participants, and implant description

Between 1993 and 1996, 58 of 60 eligible participants were recruited into a prospective, randomized clinical trial. This trial had been peer reviewed, had received ethical approval, and had taken place at the Université de Montréal's Faculty of Dental Medicine and its affiliated hospital dental department (SMH Scientific Research Committee Certificate No. PROJECT-90-01). The present article documents data collected at the 25-year (24.6 ± 0.19 years, mean \pm SE) follow-up of this within-subject trial (University of Montreal Ethics Committee Certificate No. CERC-19-015-P, ClinicalTrials.gov Identifier: NCT03862482). All study procedures were performed in accordance with the Helsinki Declaration and its later amendments, and all participants signed informed consent documents prior to inclusion into this study.

Standard Brånemark System®, Swede-Vent® and Screw-Vent® two-piece, platform-matched implants had a parallel-wall fixture/screw macro structure, with pitch height (0.6 mm) and flange angle (60 degrees) starting below their collar. (Binon, et al., 1992; De Bruyn, et al., 1992; Helsingen, & Lyberg, 1994; Niznick, 1989; Wennerberg, et al., 1993). Swede-Vent® was a clone of the Brånemark® macro design (Binon, et al., 1992; Helsingen, & Lyberg, 1994). It had an

identical 1.2mm-long external-connection machined collar requiring countersinking to place its fixture/collar border 1.2mm below, 0.6mm-long centrally located external connection above, and wider implant/abutment interface platform at the alveolar crest (De Bruyn, et al., 1992; Helsingen & Lyberg, 1994; Wennerberg, et al., 1993). Brånemark® and Swede-Vent® received a two-piece, platform-matched, parallel-wall abutment/screw unit. While the Brånemark® fixture surface was machined, Swede-Vent's® was acid etched to a 1-3µm-pitted surface. Although Swede-Vent® and Screw-Vent® fixtures were identically acid etched by the same manufacturer, Screw-Vent's® narrower 3.6mm-long machined collar did not require countersinking to place its fixture/collar border below and implant/abutment interface platform at the crest. In addition, Screw-Vent's® internal-connection, friction-fit collar design accepted a platform-matched, one-piece abutment/screw unit (De Bruyn, et al., 1992; Niznick, 1989).

Initial study design, surgical and prosthetic treatments

A statistician prepared a sampling design that included three configuration diagrams. Each diagram identified five implants of the three types, and showed how one of each type was to be placed in a cyclical, side-by-side, rotating fashion at five sites between mental foramen. In this way, an equal number of each implant type was to be placed at each of the five sites, and an equal number of participants received three of the five implants to the left or right of the midline. Configuration diagrams also documented each implant's length. Allocation concealment by the project coordinator then allowed 20 participants to receive Configuration 1, 19 had Configuration 2, and 19 had Configuration 3. Configuration diagram (but not number) was stored inside each chart, and only shown to the operating team at the time of surgery. The same surgeon ([name]) placed all implants, in a submerged fashion, with MG at the crest. Implants were 3.75mm in diameter, but the project coordinator determined implant length based on pre-operative radiographic measurements of available bone height. After approximately six months, the same surgeon exposed all implants, removed cover screws, and placed healing/prosthetic abutments. Complete seating of abutments onto implant platforms was confirmed with radiographs. Each participant received a conventional complete removable maxillary prosthesis and a fixed implant-supported mandibular prosthesis with bilateral posterior cantilever sections. Acrylic-resin teeth were processed over a casted, silver-palladium alloy framework. Gold prosthetic screws for Brånemark® and Swede-Vent® implants, and titanium screws for Screw-Vent® implants anchored the mandibular prostheses to the abutments. Participants followed an oral/implant hygiene regimen of daily mouthwash rinses, and gentle flossing and brushing with provided hygiene kits. Follow-ups occurred at one year, two years, 15 to 20 years, and 23 to 26 years

following prostheses attachment. Twenty-two participants (41.5%, age 71.1 ± 1.2 years, 11 women, 110 implants) were enrolled in the present study

Clinical and radiographic evaluation

At the 23- to 26-year recall, prosthodontists ([name] and [name]) ascertained the presence of any fractured or mobile prosthetic component. Following this assessment, the prosthodontists removed the prostheses, and abutment mobility was evaluated. Prosthesis and abutment mobility were evaluated by exerting manual pressure alternately on the handles of two instruments, each placed on opposite sides, and were recorded as absent (0) or present (1). Because abutment screws are tightened to 35N/cm of pressure using an instrument during prosthesis insertion, abutments should not be retrievable by finger pressure alone. Consequently, an attempt was also made to untighten each of the non-mobile abutments with finger pressure. If the abutment screw was retrievable, then the abutment was considered to be loose, even in the absence of visual mobility. Two calibrated examiners then performed the follow-up clinical (periodontist [name]) and radiographic ([name]) examinations, with abutments in place. All examiners were unaware of implant configurations. The dichotomous/binary plaque index (dPI) was used to document the absence (0) or presence (1) of plaque on the mesial, distal, buccal and lingual implant/abutment surfaces (Galgut, 1999). A ColorVue UNC12 Hu-Friedy probe was then used to measure (mm) the keratinized gingiva height on the buccal and lingual implant/abutment surfaces, and probing depth on the mesial, distal, buccal and lingual implant/abutment surfaces. Intra-examiner agreement for 46 sites regarding keratinized gingiva height and 100 sites for probing depth showed that 100% and 99% of measurements differed by 1mm or less, respectively. Following probing, the dichotomous/binary bleeding index (dBI) documented the absence (0) or presence (1) of bleeding at each peri-implant site on the mesial, distal, buccal and lingual implant/abutment surfaces. (Galgut, 1999). Absence (0) or presence (1) of purulence was also documented.

After having assured the stability of all abutments, radiographic evaluation of quantitative peri-implant bone healing was performed with the conventional peri-apical technique, using a standardized equipment and measurement protocol (Camarda, et al., 2018). Five peri-apical radiographs per participant were taken and numbered according to the implant site, 1 being the first on the subject's left, 5 the last on the right, and were stored in plastic film holders. In order to compare and calibrate conventional peri-apical radiology with phosphor-plate technology, the Digora System™ (Digora Optime™, Sporedex Dental Co., Tuusula, Finland) was also used with the standardized equipment to take peri-apical radiographs on 95 implant/abutment units (Bhasharan, et al., 2005). Following calibration, the distance between the first-bone-to-implant-

contact-point and the crestal-microgap (fBIC-MG) was measured (mm) at the mesial and distal aspects of each implant/abutment unit using a Schei ruler under X10 magnification on the conventional films. Adobe Photoshop® (Adobe System Incorporated, San Jose, CA, USA) was used to measure fBIC-MG on the digital radiographs acquired with phosphor-plate technology. After having taken the radiographs, all abutments were removed and cleaned, and prosthesis/framework structures were cleaned and polished. Abutments and prosthesis/framework structures were then re-inserted using recommended instrument torque. Intraclass Correlation Coefficient (ICC, two-way mixed-effect model) assessed inter-examiner and intra-examiner reliability of bone level measurement on 20 radiographs. The reliability was excellent, with an inter-examiner ICC of 0.94 and an intra-examiner ICC of 1.00. The Dahlberg measurement error was 0.38mm.

Statistical methods

Assessment was initially based on intention-to-treat. Based on a previous study (Camarda, et al., 2018), the effect size for the difference in bone level change between implant groups was expected to be 0.95. A sample size of 16 participants would, therefore, ensure an 80% power to reject the null hypothesis, if it was indeed false at a two-sided Bonferroni-adjusted α level of 0.017 (to adjust for pairwise comparisons between implant groups), using a repeated measures ANOVA. Absence or presence of prosthesis, abutment, and implant mobility was analyzed with the Fisher's exact test. The mean keratinized gingiva height (mm), probing depth (mm), and percentage of sites with dPI, dBI and purulence were calculated for each implant. Shapiro-Wilk test was used to assess the normality of data distribution. These values were then analyzed with nonparametric ANOVA-type statistic for repeated measures within subject, with implant type, site and configuration as independent variables (Brunner, et al., 2002). Quantitative bone healing was analyzed with mixed models for repeated measures within subject, with implant type, site and configuration as independent variables, and implant length as covariate. The lengths of the different implant types were compared with a Kruskal-Wallis test. Confidence Interval (CI) was established at two-sided 95% Confidence Level (CL). The level of significance was set at $p < 0.05$ and Bonferroni correction was applied for pairwise comparisons. ICC (two-way, mixed-effect model) and Bland-Altman limits of agreement (Bland, & Altman, 1986) were used to analyze comparison of mean fBIC-MG values between conventional peri-apical radiology and phosphor-plate technology. All statistical analyses were performed using IBM SPSS Statistics for Windows® Version 25 (IBM Co., Armonk, NY, USA), and SAS 9.4 (SAS Institute, Cary, NC, USA).

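### Does the lack of any stated masking to implant type call for a change to the plan for the two Screw-Vent contrasts?

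*Combined protocol and SAP*

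**What the plan says.** The only statement on masking of the examinations, under Clinical and radiographic evaluation, is "All examiners were unaware of implant configurations". The section on initial study design defines a configuration as a diagram that places the three implant types over five sites. The one concealment measure described for the diagram is that only the operating team saw it, at surgery.

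The stated objective is "Evaluate the effects of two different machined-collar lengths and designs on peri-implant healing". Under Participants, and implant description, the threads are described "with pitch height (0.6 mm) and flange angle (60 degrees) starting below their collar". Brånemark and Swede-Vent share an "identical 1.2mm-long external-connection machined collar requiring countersinking", whereas "Screw-Vent's® narrower 3.6mm-long machined collar did not require countersinking". The abutments differ along the same line: "Brånemark® and Swede-Vent® received a two-piece, platform-matched, parallel-wall abutment/screw unit", while Screw-Vent "accepted a platform-matched, one-piece abutment/screw unit". The prosthetic screws differ too: "Gold prosthetic screws for Brånemark® and Swede-Vent® implants, and titanium screws for Screw-Vent® implants anchored the mandibular prostheses to the abutments".

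The prosthodontists removed the prostheses and checked abutment mobility. The clinical and radiographic examinations followed, with abutments seated. The bone-level outcome, fBIC-MG, is the distance from the crestal microgap to the first bone-to-implant contact, read on conventional films at tenfold magnification. Statistical methods plans a mixed model with type, site and configuration as factors and implant length as covariate, 95% confidence intervals, and Bonferroni correction for pairwise comparisons.

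**The concern.** Not knowing a layout diagram is different from being unable to recognise an implant on a film. The reader measures from the microgap, so the collar lies in the field of view, and its unthreaded length is what separates Screw-Vent from the other two. A reader with an expectation about collar design could have read Screw-Vent systematically high or low. All three types sit in the same mouth, so they can be compared side by side.

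The exposure falls on two of the three pairwise contrasts, and those two carry the objective. The reliability figures do not settle the matter: ICCs of 0.94 and 1.00 measure agreement, and readers who can all see the type can agree and share a bias. A shift need not be large to distort the test. With no true difference, 22 paired observations and alpha 0.017, a systematic shift of 0.2 or 0.3 SD of the paired difference would raise the false-positive rate from 1.7% to 6.6% or 14.2%.

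**Working it through.** **1. Is Screw-Vent recognisable on the films?** The extra unthreaded length is 3.6 − 1.2 = 2.4 mm. At a pitch of 0.6 mm this is 2.4 / 0.6 = 4 thread pitches, on a collar that is also narrower. Recognition is probable. This is an inference from the geometry; the documents do not report that it happened.

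**2. Do the other cues reach the readers?**

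| Cue | Who could see it | Supported? |
|---|---|---|
| Collar length and width | Radiographic reader | Probable |
| Gold or titanium prosthetic screw | Prosthodontists, at prosthesis removal and the mobility check | At most there; the prostheses were off before the periodontist examined |
| One-piece or two-piece abutment unit | Clinical and radiographic examiners | Nothing says that seated units look different |

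The text also does not say that the original abutments and screws were still in use. The concern narrows to the film reader.

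**3. What does the masking sentence claim?** A configuration is a placement of types over sites. Being unaware of it can mean not having seen the diagram, or not knowing which type sat where. On the second reading the sentence asserts masking to type without saying how it was achieved.

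**4. The plan's own figure.** Inputs from Statistical methods: effect size 0.95, two-sided alpha 0.017, 80% power, 16 participants. A paired t test (noncentral t, 0.95 in SD of the paired difference) has power 0.819 with 15 participants and 0.852 with 16. A three-level repeated-measures F test (extremes 0.95 SD apart, third mean midway, assumed correlation 0.5) has power 0.802 with 16. The stated 16 is reproduced.

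**5. How large a shift would matter?** A constant shift on all Screw-Vent readings is a multiple of the Screw-Vent indicator, which is already a fixed effect. It moves both Screw-Vent contrasts one for one and leaves their standard errors and Brånemark versus Swede-Vent unchanged. The shift needed to remove significance is therefore

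- threshold = observed effect − t × SE, with SE = √(l′(X′V⁻¹X)⁻¹l).

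Assumptions: 22 participants with 110 implants; a cyclic layout (ABCAB, BCABC, CABCA) split 8/7/7; type, site and configuration in X; length omitted; equal correlation within participant; 0.95 in per-implant SD units and observed exactly as planned. The critical value at alpha 0.017 is 2.592 on 21 df and 2.437 on 81 df, where 110 − 22 − 2 − 4 − 1 = 81 leaves one df for length.

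| Correlation | SE | Threshold, 21 df | Threshold, 81 df |
|---|---|---|---|
| 0.3 | 0.200 | 0.95 − 2.592 × 0.200 = 0.43 | 0.95 − 2.437 × 0.200 = 0.46 |
| 0.5 | 0.169 | 0.95 − 2.592 × 0.169 = 0.51 | 0.95 − 2.437 × 0.169 = 0.54 |
| 0.7 | 0.131 | 0.95 − 2.592 × 0.131 = 0.61 | 0.95 − 2.437 × 0.131 = 0.63 |

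At correlation 0.5 this is 54% to 57% of the planned effect. Treating the data as 22 single pairs would give SE = √(2 × 0.5 / 22) = 0.213 and a threshold of 0.95 − 2.592 × 0.213 = 0.40. That understates the tolerance, because the model uses five implants per participant, about 37 per type.

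**The case for a change.** The best case for a change is that recognition on the films is probable, that it touches the contrasts the trial exists to estimate, and that the remedy is cheap: a limitation sentence, plus Bonferroni-adjusted limits beside two contrasts so that readers can judge how much bias the result would tolerate.

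Part of this stands. The collar was probably visible, agreement statistics do not exclude shared bias, and the investigators could usefully say whether, and how, the film reader was masked to type.

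The rest is weaker. The documents do not support a statement that masking covered the diagram only. The file is a methods text without results or discussion, and a limitation would normally appear in a discussion, so its absence here does not show an omission. Statistical methods already applies Bonferroni to pairwise comparisons and does not say whether the pairwise intervals are adjusted, so the adjusted limits may already be covered. The threshold handles only a constant shift and says nothing about a bias that varies with bone level.

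One further caveat concerns Brånemark versus Swede-Vent. Swede-Vent copies the Brånemark macro design, which protects this contrast. Under a strict cyclic order, however, the Screw-Vent sites identify the configuration, so the protection assumes that the reader did not know the rotation.

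**Conclusion.** The masking sentence is unsubstantiated as regards implant type, and Screw-Vent was probably recognisable to the film reader. That is a limitation of two of the three contrasts, not an error in the plan. The collar is the treatment under study and the microgap must be visible for the measurement, so disclosure is the realistic response; it alters no film, reading, model or estimate.

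Nothing in the documents gives the size or direction of a reading bias. The illustrative threshold is 0.51 to 0.54 SD at correlation 0.5, and 0.43 to 0.63 SD for correlations from 0.3 to 0.7. It rests on an observed effect of 0.95 per-implant SD, the assumed 8/7/7 cyclic layout, omission of length, and a constant shift. It measures tolerance and does not estimate bias. Authors can cover the point with one hedged sentence on the radiographic contrasts when they report.

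### Does an intention-to-treat label on a 25-year analysis of 22 of the 58 allocated participants, with a stated 41.5%, call for a change to the plan?

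*Combined protocol and SAP*

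**What the plan says.** The section on participants and implants reports that between 1993 and 1996 "58 of 60 eligible participants were recruited into a prospective, randomized clinical trial". It presents the current report as the 25-year "follow-up of this within-subject trial", under its own ethics certificate. The abstract confirms the timing: "Peri-implant bone levels were measured after 23 to 26 years of function".

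The section on the initial study design gives the allocation. "Each diagram identified five implants of the three types", and concealed allocation "allowed 20 participants to receive Configuration 1, 19 had Configuration 2, and 19 had Configuration 3". After the prostheses were attached, "Follow-ups occurred at one year, two years, 15 to 20 years, and 23 to 26 years". The section ends with the 25-year sample: "Twenty-two participants (41.5%, age 71.1 ± 1.2 years, 11 women, 110 implants) were enrolled in the present study". The denominator of that percentage is not given.

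Statistical methods opens with "Assessment was initially based on intention-to-treat" and does not say what the phrase covers or what replaced an initial basis. Bone level is then analysed with a within-subject mixed model. Its terms are implant type, site and configuration, with implant length as covariate; there is no visit term.

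**The concern.** Intention-to-treat is usually taken to mean that everyone allocated is analysed as allocated. Here 58 were allocated and 22 supply 25-year data. Because the model has no visit term, a participant without a 25-year reading contributes nothing to it. Taken over all those allocated, the label cannot describe the 25-year analysis.

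The percentage adds to the unease. It matches neither total in the document and is more favourable than the proportion of those allocated. Together, the label and the figure could lead a reader to picture a broader and better-retained population than the one analysed. At stake is whom the result describes. If people stayed away for reasons linked to how differently the implant types fared in their own mouths, the type contrast itself would also be at stake.

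**Working it through.** **Inputs.** Allocated: 20 + 19 + 19 = 58, of 60 eligible. In the 25-year study: 22 participants, 110 implants, stated share 41.5%. Implants planned per participant: 5. Planned sample size: 16.

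**1. Reproducing 41.5%.** With numerator 22, a share that rounds to 41.5% needs a base between 22/0.4155 = 52.95 and 22/0.4145 = 53.08. The only whole number is 53: 22/53 = 41.5%, against 22/52 = 42.3% and 22/54 = 40.7%.

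**2. Against the stated totals.** 22/58 = 37.9% and 22/60 = 36.7%. A miscounted numerator does not explain the figure: 24/58 = 41.4% and 25/58 = 43.1%; 24/60 = 40.0% and 25/60 = 41.7%.

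**3. Counting implants.** 58 × 5 = 290 planned, and 110/290 = 37.9%. A share of 41.5% needs 265 implants (110/265 = 41.5%), and 265 = 53 × 5. The implied base is again 53 participants.

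**4. Size of the discrepancy.** 58 − 53 = 5 participants are outside the implied base, and 41.5 − 37.9 = 3.6 percentage points separate the two shares. Absent at 25 years: 58 − 22 = 36, and 36/58 = 62.1%. The document does not say what the 53 are. It contains an objective and methods only, with no participant flow, so the figure may be correct on a base explained elsewhere.

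**5. What each reading of the sentence does to the analysis.**
- *Implants compared by allocated type among those who attended.* The model uses the 22 participants. Since 22 × 5 = 110, every planned implant of every attender is counted.
- *A reference to the original trial.* The 25-year model still uses the same 22 participants and 110 implants.
- *All 58 analysed at 25 years.* The described model cannot do this, and the text gives the enrolled number as 22, so no analyst would be led to it.

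The first two readings could differ only if some implants were not of the type on the diagram, and the document reports no such departure.

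**6. What the loss does to the type contrast.** Write a bone-level reading as a participant effect, plus a type effect, plus site and other terms. All three types are in each mouth, so the participant effect cancels from the difference between two types. Attendance linked to general health, age or overall bone level, but not to the difference between types, leaves the contrast alone. Bias needs attendance to be linked to the within-mouth difference itself. Uneven loss across the three configurations would disturb the balance of types over sites, but site and configuration are both in the model.

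**7. What extra analysis could add.** A longitudinal model would need bone readings from the earlier visits. The visits are listed, but no section confirms that readings from them are available for this analysis. The model would also help little if attendance depended on the unseen current difference. A comparison of earlier type differences between 22 attenders and all 36 absentees would be imprecise. Its 95% half-width is t(0.975, 56) × √(1/22 + 1/36) = 2.003 × 0.271 = 0.54 SD, and its power to detect a gap of 0.5 SD is 44%.

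**The case for a change.** The strongest case for a change is this. The only percentage printed is the more favourable one, it has no denominator, and it stands in the same report as an intention-to-treat claim. A reader should not have to work back to 53, and five participants drop out of the base without explanation. Stating the base and naming the set as available participants would cost a few words and need no new data. The protection from the within-subject design is also not complete: with 62.1% absent, nothing in the document rules out attendance that depended on the difference between implant types.

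Most of this is true as description. The label is ambiguous and the base is unstated. But an unstated denominator is not a wrong one, and a sentence with two workable readings does not contradict the counts. The population is not concealed, because 58 and 22 are both given and anyone can form 37.9%. The possibility of selective attendance stands, but it applies to any recall after some 25 years, and no wording would remove it. The document gives no evidence of its presence, size or direction. The analyses that might probe it rest on readings not known to be available and, as calculated, would be weak.

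**Conclusion.** No change to the plan is needed. There is a gap in definition that analysts fill sensibly, plus a missing denominator of the kind put right when results are reported. Followed as written, the plan compares implant types within the mouths of the same 22 participants and 110 implants, whichever workable reading is given to the intention-to-treat sentence. The 22 exceed the 16 planned, so the stated sample size is met.

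The discrepancy is 37.9% against 41.5%, or 3.6 percentage points, in a figure that enters no test or estimate. Anyone citing the trial should describe the result as that of 22 of 58 allocated participants seen at 25 years.

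The conclusion rests on three things: each participant received the implants on the assigned diagram, as the document describes; the 22 are the participants analysed; and no link is shown between attendance and the within-mouth difference between types. The last is not established by the documents. Evidence of such a link would raise a question about the result, which rewording the label would not answer.

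### Cheap improvement: Holm on the same three pairwise p-values would control the same family-wise 0.05 as plain Bonferroni with slightly more power, with one added sentence on which pair answers the collar question

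*Combined protocol and SAP*

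**What the plan says.** The Objectives line of the summary gives one aim: "Evaluate the effects of two different machined-collar lengths and designs on peri-implant healing". The summary's Material and Methods says that the 3.6 mm-collar implant (Screw-Vent) "was compared to two implants that had an identical 1.2mm-long external-connection machined collar, but one had the microtextured surface while the other's was machined". Neither comparator is ranked above the other.

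The implant description that follows says what each pair shares:

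- Screw-Vent and Swede-Vent: "Although Swede-Vent® and Screw-Vent® fixtures were identically acid etched by the same manufacturer". Their collars differ in length and width, and only the 1.2 mm collar needs countersinking. Screw-Vent's "internal-connection, friction-fit collar design accepted a platform-matched, one-piece abutment/screw unit", and the treatment section gives it a different prosthetic screw metal.
- Swede-Vent and Brånemark: "Swede-Vent® was a clone of the Brånemark® macro design", with an identical collar. The surfaces differ: "While the Brånemark® fixture surface was machined, Swede-Vent's® was acid etched".
- Screw-Vent and Brånemark: both collar and surface differ.

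Statistical methods enters implant type as a single factor in a mixed model for bone level and applies Bonferroni to the pairwise comparisons. The sample size is calculated at a "two-sided Bonferroni-adjusted α level of 0.017 (to adjust for pairwise comparisons between implant groups". It rests on the statement that "the effect size for the difference in bone level change between implant groups was expected to be 0.95", without saying which pair that refers to. Confidence intervals are set at 95%, without saying whether the pairwise ones are adjusted.

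**The concern.** There are two linked points.

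The first is efficiency. Bonferroni holds every pair to 0.05/3 even after another pair has been rejected. Holm relaxes the threshold step by step at the same family-wise error, using p-values that the analysis already produces.

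The second is interpretation. The objective concerns the collar, but the three pairs carry different information about it, and Statistical methods does not connect them to the objective. If Screw-Vent versus Brånemark were the only significant pair, the result could come from collar, surface or both, and the plan does not say how to read it. What is at stake is a few points of power at most, and clarity in an outcome that is uncommon at the planned effect.

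**Working it through.** **Inputs.** From Statistical methods: family-wise 0.05, per-pair 0.017 two-sided, effect 0.95, 16 participants, 80% power. From the treatment section: 22 participants enrolled at 25 years. Assumptions: 0.95 is in units of the SD of the within-participant difference (the documents do not state the standardiser); one mean per implant type per participant; the same SD of difference for every pair; paired t for each pair. This simplifies the planned mixed model with site, configuration and length.

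**1. The plan's own figures.** 0.05/3 = 0.01667, which rounds to 0.017, so three pairs share the error equally. The pairs are not listed; this is inferred from the number. Paired-t power uses a noncentral t with n - 1 degrees of freedom and noncentrality 0.95 × √n. At 0.017 it is 0.819 for n = 15 and 0.852 for n = 16. The stated 16 therefore exceeds 80% on this reading. At n = 22 power is 0.961 (0.960 at exactly 0.05/3).

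**2. Why Holm loses nothing.** Order the p-values and compare them in turn with 0.05/3 = 0.0167, 0.05/2 = 0.025 and 0.05/1 = 0.05, stopping at the first failure. Any p-value at or below 0.0167 passes at whatever step it falls, so every Bonferroni rejection is kept. The one exception comes from rounding: a smallest p-value between 0.01667 and 0.017 would pass the rounded threshold and fail Holm's first step. In simulation (100,000 to 200,000 trials per case) no rejection at 0.05/3 was lost. With no differences at all, family-wise error at n = 22 was 0.045 for both methods.

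**3. Power for Screw-Vent versus Swede-Vent, n = 22.**

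| True collar-pair effect | Where Brånemark lies | Bonferroni | Holm |
|---|---|---|---|
| 0.95 (planned) | equal to Swede-Vent | 0.960 | 0.972 |
| 0.95 | midway | 0.960 | 0.962 |
| 0.95 | equal to Screw-Vent | 0.960 | 0.973 |
| 0.6 (assumed) | equal to Swede-Vent | 0.590 | 0.627 |
| 0.6 | midway | 0.591 | 0.603 |
| 0.6 | equal to Screw-Vent | 0.589 | 0.627 |

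The gain is 0.2 to 1.3 points at 0.95 and about 1 to 4 points at 0.6. If Brånemark lay 0.475 beyond Swede-Vent, power at 0.95 would go from 0.961 to 0.986.

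**4. The price.** Suppose surface has an effect and collar has none. The collar pair's false-rejection rate is 1.7% under Bonferroni. Under Holm it is 3.8% at a surface effect of 0.74, about 4.7% at 0.95 and 4.8% at 1.00.

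**5. The ambiguous pattern: Screw-Vent versus Brånemark alone significant.** With no collar effect and a surface effect of 0.95, this occurs in 3.0% of trials under Bonferroni and 1.8% under Holm.

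The remaining figures illustrate effects that are not in the documents, all under Bonferroni at n = 22:

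- Surface effect 0.74 (detectable with 80% power at n = 22): 11%. In a further 68% the surface pair is significant too and the collar pair is not, which points to surface.
- Surface effect 0.6: 16%. A pure collar effect of 0.6 produces the same pattern equally often, so the pattern cannot tell the two causes apart.
- Surface effect 0.55: about 17%, the peak over surface effects.
- A total of 0.74 split 25/75 or 50/50 between collar and surface: 29% to 40%. A collar claim would then be under-supported, not false.

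**The case against.** The strongest reply is that nothing needs repair. Bonferroni is valid, 22 participants give 0.96 power at the planned effect, and Holm adds about one point. Against the worry that surface might be mistaken for collar, Holm even works in the wrong direction: at a surface effect of 0.95 it adds about 3 points of false collar findings (4.7 - 1.7). It also gives up simple simultaneous intervals. Because the text reports data already collected, a switch now would be post hoc. All of this stands. It limits the point to a modest improvement, but Holm still has the same family-wise guarantee and loses no rejection at 0.05/3.

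It can also be said that the collar comparison is not absent. The summary sets Screw-Vent against both 1.2 mm implants, and the implant description lets a reader work out what each pair shares. Screw-Vent against both, with the third pair as a surface check, is a coherent reading. That too stands: what is missing is a sentence in Statistical methods. The source of the 0.95 may name a pair, but it is not available here.

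A reader might infer more: that the plan cannot answer its objective, or that it is likely to report a surface effect as a collar effect. The documents support neither. No passage proposes a collar claim from Screw-Vent versus Brånemark alone, the three tests read together often separate the factors, and the ambiguous pattern is rare at the only effect size given.

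**Conclusion.** The point holds as a cheap improvement, not as an error. The plan's multiplicity control is correct and its sample size is adequate on the paired-difference reading. Holm is uniformly at least as powerful as Bonferroni at 0.05/3, with a small gain at the planned effect and a somewhat larger one at smaller effects. The accompanying rise in the collar pair's own error stays inside the family-wise 0.05.

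Holm's validity and its dominance over Bonferroni do not depend on the simulation. The power and error figures do rest on the paired-t simplification, equal SDs of difference and, apart from 0.95, assumed effects.

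Screw-Vent versus Swede-Vent should not be read as isolating collar length. It compares collar design as a package, because connection, collar width, countersinking, abutment and prosthetic screw also differ. It is nevertheless the only pair free of the surface difference.

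**What to change.** 1. For the pairwise fBIC-MG comparisons, replace plain Bonferroni with Holm on the same three p-values. Show Bonferroni intervals at 1 - 0.05/3 = 98.3% beside them and state that level.
2. Unless a record shows that Holm was chosen before the results were seen, label it post hoc and report the Bonferroni result alongside.
3. Add wording to Statistical methods: the collar conclusion rests on Screw-Vent versus Swede-Vent, described as collar design as a package; Swede-Vent versus Brånemark is the surface check; Screw-Vent versus Brånemark alone cannot support a collar conclusion.

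Item 1 re-adjusts three existing p-values and needs no new data or model. Its costs are the higher error rate for the collar pair under a pure surface effect and the lack of simple simultaneous intervals from Holm, which is why the 98.3% intervals are shown. Item 2 costs an extra column or footnote. Item 3 is text only; its one consequence is that Screw-Vent versus Brånemark loses standing as collar evidence.
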